#### 6.2.2 Blinded assessor

We will employ centralized, blinded outcome assessors, who are comprehensively trained SLP graduate students located at UofSC, to score the videorecorded primary outcome measure (VPM) for all study subjects. Twenty percent of the assessments, including baseline testing and outcome measures, will be scored by a second, independent SLP graduate student assessor to establish inter-rater reliability. In addition, each SLP graduate student assessor will rescore at least 20% of all assessments, for which they were the original primary scorer, to establish intra-rater reliability. Our team has ample experience with aphasia assessments and every measure will be taken to maximize reliability of outcome testing. The primary and secondary coding SLP graduate student assessors will be blinded to the treatment arm. They will also be blinded to when the behavioral measures were obtained (i.e., there will be no time stamps on the assessments, and the assessor will not know if the sample was obtained before SET or no SET, or at which time point after SET or no SET they were obtained).

# 6.3 Study Intervention Compliance

#### 6.3.1 Subject enrollment, subject assessment, and data entry fidelity

Across all project sites, we will standardize the training of SLPs and trained research staff who administer the cognitive-linguistic and outcome testing, beginning with the development of an assessment manual. We will monitor adherence to assessment administration procedures throughout the 5-year project period. Transcription and scoring of the video and discourse measures will be accomplished in the lab at UofSC, with the exception of transcription and scoring of the ASRS 3.0, which will be completed by an expert scorer at UoU. All discourse assessment sessions will be videorecorded and coded with a unique identifier and uploaded to Box. Scores from videos will be recorded on Case Report Forms (CRFs) maintained in WebDCUTM. To maintain reliability, at least 20% of all videorecorded discourse sessions will be re-scored by an SLP.

# 6.3.2 Participant treatment fidelity

Standardized clinician and research staff training relying upon a detailed manual of treatment procedures will be implemented. Similar to the assessment manual, the purpose of explaining the project and emphasizing the importance of treatment activities is to promote clinician buy-in and subsequent adherence to procedures. The administration of SET is probably no more complex than that of aphasia treatment approaches practiced in everyday clinical practice; it is simply operationalized so that procedures will be standardized across subjects and sites.

#### 6.3.3 Testing and treatment fidelity

It is imperative that we guard against the following threats at each site: variability in clinician and research staff qualifications, drift (gradual change in study procedures over time), contamination (systematic or variable influence of outside factors not controlled for in the study design), and clinician/research staff turnover. A Program/SLP Manager from MUSC will oversee testing and treatment fidelity procedures across all sites.

Ratings of testing/assessment video recordings will be conducted by a Program/SLP Manager or another experienced SLP at MUSC. The rater will observe assessment and treatment video recordings for SLPs across each study site, document fidelity adherence via the SpARc SLP Assessment and Treatment Fidelity Observation Forms, and provide written feedback to clinicians to ensure fidelity of assessment and treatment administration across sites. If necessary, additional training and support will be provided to clinicians by the Program/SLP Manager or another experienced SLP at MUSC.

# 7.0 Study Intervention Discontinuation and Participant Discontinuation or Withdrawal

#### 7.1 Discontinuation of Study Intervention

The Principal Investigator (PI) at each site has the authority to discontinue a person's participation in the trial at any time if in the participant's best interest; however, the failure to adhere to the study protocol should not be considered a reason for withdrawing a participant from the study. All participants randomized will be included in the analysis, and participants

who withdraw from the study will not be replaced. Participants who wish to discontinue the study intervention or who do not return for follow-up visits should be contacted about participating in follow-up visit(s), so that at a minimum the primary outcome can be collected.

#### 7.2 Participant Discontinuation/Withdrawal from Study: Instructions

- During initial consent, it will be made clear that protocol adherence is of utmost importance to participation in the trial. This is clearly stated in the consent document.
- During the trial, if the participant is not adhering to protocol (e.g., excessive tardiness and cancellations), this will be discussed with the participant and caregiver.
- If the participant still does not comply, the PI will be notified.
- The PI has the final decision to discontinue participation due to safety reasons.

The participant can decide to withdraw at any time. If the participant withdraws from the study voluntarily:

- The PI will be notified.
- Withdrawal status will be appropriately documented, per IRB regulations
- If they chose not to withdraw and still have missed appointments, we will continue the intervention until the planned duration while recording the number of missed appointments. We will utilize the number of missed appointments for statistical analysis. Refer to section 9.4.4.

#### 7.3 Lost to Follow-up

A large number of our participants have already participated in previous aphasia studies and know that new studies will likely be available to them in the future; therefore, we typically get a small group of people that are lost to follow-up. All sites are also active in the local community, hosting events and support groups to advocate for those with aphasia. This is also beneficial and reduces the number of those lost to follow-up.

# 8.0 Study Assessments and Procedures

#### 8.1 Efficacy Assessments

#### 8.1.1 Baseline measures

The WAB-R will be obtained at participant screening to determine if the participant fits criteria for non-fluent aphasia (WAB-R Comprehension score > 4 and WAB-R Fluency score < 6). See Table 6 for aphasia classification chart. If the participant does not classify as having non-fluent aphasia, this is considered a screen failure. The participant will undergo an MRI to determine stroke eligibility criteria, unless MRI images from the stroke are made available to the study team for review. The ASRS 3.0, PPTT, and WAIS-III will be obtained for the purpose of linguistic assessments and participant description in publications. The ASRS 3.0 measures the presence and severity of AOS; the PPTT assesses amodal semantic processing of nouns; and the WAIS-III measures non-verbal abstract problem solving and inductive and spatial reasoning. The SAQOL-39g will be given to assess quality of life for each individual with aphasia. All baseline language assessments will be videorecorded for offline scoring. Recording will include the participant from head to torso, and all recordings will be stored on Box.

Speech repetition and comprehension: We will employ detailed measures of speech repetition and comprehension to refine the identification of subtypes of aphasia and improve the evaluation of the influence of these variables on the effectiveness of SET. As part of the WAB-R, participants will complete the repetition subtest involving single words, phrases, as well as shorter and longer sentences. In addition, all participants will be administered the PRT, involving real words. For detailed assessment of auditory comprehension, we will rely on subtests from the WAB-R.

The mechanisms of action of SET will be determined from the comprehensive behavioral assessment as described in Table 1 above. More specifically, we will define whether fluency improvements with SET are supported by repetition, speech comprehension, or residual fluency, based on the multi-faceted speech and cognitive evaluations.

#### 8.1.2 Primary outcome – VPM

All recorded discourse measures will be stored on Box and scored centrally in the lab at UofSC using automated coding analysis systems available through AphasiaBank. We have already used this setup to assess outcome in our original study of speech entrainment. AphasiaBank includes computerized tools to accomplish discourse transcription and analyses, such as Codes for the Human Analysis of Transcripts (CHAT) and Computerized Language Analysis (CLAN).

Speech samples for VPM scoring will be assessed through procedural storytelling and narrative – with four items in each category. The procedural storytelling items are: 1) how to make a peanut butter and jelly sandwich, 2) how to make scrambled eggs, 3) how to brew coffee, and 4) how to wash dishes. The subject will be recorded while describing each procedure. A two-minute time limit will be imposed for each item. The four topics will be randomized with only one topic being presented each time VPM is being assessed without topic repetition. Randomization of topics will be performed in WebDCUTM.

The narrative items will be: 1) Cinderella story, 2) Little Red Riding Hood, 3) The Three Little Pigs, and 4) Goldilocks. The participant will be provided with a picture book without text to guide and serve as a reminder of the story, and the participant will be asked to recount the passages of the story as depicted in the book. Similarly, one narrative will be presented at each VPM assessment, and they will be randomized for each participant in WebDCUTM.

By combining procedural storytelling and narratives ranging from different topics, a broad sample of discourse abilities will be obtained. They will be scored using automated coding analysis (CLAN) systems available through AphasiaBank. Words Per Minute (WPM) is included in AphasiaBank and our data will be compared against the data from >440 aphasic subjects already included in AphasiaBank. This feature is especially important for determining variance across participants. The outcome assessor will be blinded to group assignment and to when the sample was acquired (at baseline or after each treatment interval).

#### 8.2 Adverse Events and Serious Adverse Events

\* Refer to MUSC IRB Human Research Protection Program (HRPP) Guide, Unanticipated Problems and Adverse Events Policy and Procedures, section 4.7 found at https://research.musc.edu/resources/ori/irb/forms.

#### 8.2.1 Definition of Adverse Event

An AE or adverse experience is any untoward or unfavorable medical occurrence in a human subject, including any abnormal sign (e.g., abnormal physical exam or laboratory finding), symptom, or disease, temporally associated with the subject's participation in the research, whether or not considered related to the subject's participation in the research. AEs encompass both physical and psychological harms and occur most frequently in the context of biomedical research, although they can occur in the context of social and behavioral research.

An internal AE is an SE experienced by subjects enrolled by the investigator(s) at MUSC or at a site for which MUSC has oversight.

An external AE is an AE experienced by subjects enrolled by investigators at other institutions engaged in a multi-site clinical trial.

#### 8.2.2 Definition of Serious Adverse Events

A serious adverse event (SAE) is any AE temporally associated with the subject's participation in research that meets any of the following criteria:

- Results in death
- Is life-threatening (places the subject at immediate risk of death from the event as it occurred)
- Requires participant hospitalization or prolongation of existing hospitalization
- Results in a persistent or significant disability/incapacity
- Results in a congenital anomaly/birth defect
- Any other AE that, based upon appropriate medical judgment, that may jeopardize the subject's health and may require medical or surgical intervention to prevent one of the other outcomes listed in this definition (examples of such events include allergic bronchospasm requiring intensive treatment in the emergency room or at home, blood dyscrasias or convulsions that do not result in participant hospitalization, or the development of drug dependency or drug abuse).

#### 8.2.3 Adverse Event and Serious Adverse Event Reporting

AEs will be documented in the participant's chart. An AE will only be reported if it is related to the intervention. The relation to intervention will be determined by the site PI. SAEs will be documented in the participant's chart AND reported.

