#### 2.3.3 Participant Testing & Treatment

In our experience, occasional participants will have a negative reaction to neuropsychological testing. For example, this can be caused when participants realize that their performance on a given test is far worse than they would have expected. We always make sure that ample time is allotted for neuropsychological testing and that participants are allowed

breaks as needed. With regard to the behavioral treatment, the only adverse reaction that we occasionally see is fatigue. This is something that we warn participants about ahead of time.

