# 3.0 Objectives and Endpoints

Objectives	Endpoint	Justification			
Primary					
To estimate the dose of SET for individuals with non-fluent aphasia that has the highest effect size on VPM.	Verbs per minute (VPM) at 3 months post-treatment/control period.	*See justification below			
Secondary					
To estimate the dose of SET for individuals with non-fluent aphasia that has the highest effect size on SAQOL-39g.	SAQOL-39g at 3 months post- treatment/control period	To assess if improvements in fluency from SET are related to gains in quality of life.			
Safety and Tolerability	Safety and Tolerability				
To assess the tolerability and safety of SET	Number of treatment sessions completed	Adequate tolerability would be completion of at least 80% of the treatment sessions.			

Exploratory	Adverse Events possibly/probably/definitely related to study treatment and Serious Adverse Events	Although this study intervention is low-risk, there is the potential for risk in any clinical trial.
To estimate the dose of SET for individuals with non-fluent aphasia that has the highest effect size on the WAB-R, CETI, and ASRS 3.0.	Scores at 3 months post-treatment/control period.	To assess if improvements in fluency from SET are related to gains in other speech and/or quality of life measures.
To estimate the effect of SET on VPM, WAB-R, SAQOL-39g at early and late time points.	1-week post and 6 months post	The primary time point of interest is the 3 months post, but the 1 week and 6 month post assessments will be explored to assess whether benefits are sustained over time

\*The primary endpoint for this trial is VPM at three months post-conclusion of SET or control. VPM is a measurable representation of spontaneous speech production. This primary endpoint was chosen for the following reasons:

- 1) Spontaneous speech is an important "real-life" aspect of language. It has a direct effect on conversation and social aspects of language, and directly informs on practical and meaningful elements of communication.
- 2) The use of verbs during spontaneous speech provides a reliable measure of language abilities and effectiveness of communication.
- 3) It is not surprising that many individuals with aphasia can achieve improved fluency during the SET session. However, for SET to have a clinical impact, it should lead to sustained benefits that remain after the therapy. Benefits that can last at least 3 months after therapy are highly important.

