#### 9.4.6 Safety Analyses

Monitoring Plan for Worsening in the Primary Outcome: If SET leads to substantially worse outcome than the no SET arm, early stopping may be considered. The unblinded statistician will fit the primary analysis model semi-annually in order to compare VPM between the combined SET durations versus No SET (one-sided  $\alpha$ =0.025). As part of this analysis, outliers will be explored to ensure that the results are not driven by a specific individual. Should the null hypothesis be rejected, an investigation of dose response among the SET arms based on qualitative evaluation (i.e. not statistical) when ordered in terms of dose level will occur. Should a dose response relationship be detected, the unblinded statistician will bring this to the attention of the DSMB and investigators.

All AEs and SAEs are summarized by preferred term according to the Medical Dictionary for Regulatory Activities (MedDRA) adverse reaction dictionary in terms of frequency of the event, number of subjects having the event. For the Closed DSMB report, severity, and relatedness to the treatment will also be shown by treatment group.

At the end of the trial, the cumulative incidences of the specific SAEs related to treatment, as well as all SAEs, will be compared across groups.

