### **Safety Monitoring**

The unblinded statistician at the DCU will produce semi-annual DSMB reports and at the request of the DSMB. The Closed Session DSMB reports will show tables by partially blinded treatment group. All serious adverse events will be summarized by “preferred term” and associated system-organ class according to the MedDRA dictionary and by treatment group in terms of frequency of the event and number of subjects having the event. For the DSMB report, severity and relatedness to the study drug will also be shown by treatment group.

At the end of the trial, the cumulative incidences of the specific SAEs related to treatment, as well as all SAEs, will be compared across groups.

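### The relatedness filter on non-serious AEs, if it governs entry in the trial database, leaves no interpretable SET versus no-SET comparison of those events; the SAP omits them in any case

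*Protocol*

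**What the plan says.** Protocol section 8.2.3 separates charting from reporting. For AEs in general, "AEs will be documented in the participant's chart", but "An AE will only be reported if it is related to the intervention", and "The relation to intervention will be determined by the site PI". For serious events there is no such condition: "SAEs will be documented in the participant's chart AND reported".

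Other sections bear on the same data:

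- Section 8.2.1 defines an AE without regard to relatedness.
- Section 1.3.3.1 has SET participants asked about AEs at the end of each treatment week and no-SET participants telephoned weekly for the same purpose. Section 6.1.1 says the no-SET arm receives no specific therapy from the study.
- Section 3.0 gives the safety endpoint as "Adverse Events possibly/probably/definitely related to study treatment and Serious Adverse Events".
- Section 9.4.6 promises that "All AEs and SAEs are summarized by preferred term", with severity and relatedness by treatment group in the closed DSMB report. Its end-of-trial comparison across groups covers treatment-related SAEs and all SAEs.
- SAP section 12, under Safety Monitoring, is narrower: "All serious adverse events will be summarized by" preferred term and organ class. It repeats the end-of-trial SAE comparison and does not mention non-serious AEs.

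**The concern.** In an arm with no study therapy there is almost nothing for an event to be related to. A relatedness condition applied before data entry would remove nearly all non-serious control events and keep some of those in the SET arms. The by-arm table would then mix true event rates with attribution decisions. Those decisions are probably made with knowledge of the arm: section 4.1.1 says research staff are not blinded, which I take to include the site PI, although the PI is not named there.

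The events affected are the ones this trial is most likely to see. Section 2.3.3 says that with behavioural treatment "the only adverse reaction that we occasionally see is fatigue", and fatigue is ordinarily non-serious. Table 1 schedules the numerical fatigue rating (NRS-FRS) at baseline only, so AE collection is the route by which fatigue during treatment would be recorded. A trial choosing among three treatment durations should be able to describe such events against its control.

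**Working it through.** The documents state no AE rate and no AE-based sample size, so there is no figure of the plan's own to reproduce. The check has two parts.

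**1. What the filter would do if it governs the database**

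Inputs from the documents: 1:1:1:1 allocation of 80 participants, so 60 on SET and 20 on no SET.

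Assumptions, not in the documents:
- background risk p of a non-serious AE, equal in all arms (no true effect): 10% to 50%
- share a of SET-arm events judged related: 10% to 50%
- share c of control events judged related: 0, then 1% to 10%

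Expected reported events are 60 × p × a on SET and 20 × p × c on no SET. With c = 0 the artefactual gap is p × a. SET counts out of 60, with the gap against 0/20 in percentage points:

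| p | a = 10% | a = 30% | a = 50% |
|---|---|---|---|
| 10% | 0.6 (1) | 1.8 (3) | 3.0 (5) |
| 30% | 1.8 (3) | 5.4 (9) | 9.0 (15) |
| 50% | 3.0 (5) | 9.0 (15) | 15.0 (25) |

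Without the filter the expected counts would be 6/60 v 2/20, 18/60 v 6/20 and 30/60 v 10/20, a gap of zero in each row.

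Allowing some control events to be called related changes little. The expected control count runs from 20 × 0.10 × 0.01 = 0.02 to 20 × 0.50 × 0.10 = 1.0. The chance of no reported control event, (1 − p × c)^20, runs from 98% down to 36%.

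Nor can the true difference be recovered from the filtered counts. With a control risk of 30%, an expected 6/60 v 0/20 (10% v 0%) arises from each of these:
- true difference 0, one third of SET events judged related: 0.30 × 1/3 = 0.10
- true difference +10 points, only the excess judged related: 0.10 × 1 = 0.10
- true difference +20 points, half of the excess judged related: 0.20 × 0.5 = 0.10
- true difference −10 points, half of all SET events judged related: 0.20 × 0.5 = 0.10

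**2. What the SAP covers, whatever reporting means**

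| Event class | Protocol 3.0 endpoint | Protocol 9.4.6 | SAP 12 |
|---|---|---|---|
| Non-serious, related | yes | summarised | absent |
| Non-serious, unrelated | no | summarised | absent |
| SAE, all causes | yes | summarised and compared | summarised and compared |

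SAP section 10 analyses session participation, which is the tolerability endpoint, not adverse events. The related non-serious part of the safety endpoint therefore has no SAP analysis.

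**The case against.** The strongest objection is that section 8.2.3 does not say to whom an AE is reported. Section 8.2 opens by pointing to the IRB's policy on unanticipated problems and adverse events, and section 8.2.1 splits events by institutional oversight. Read as a rule for IRB reporting, 8.2.3 is compatible with a summary of all AEs and with the weekly control calls. This stands as a possible reading, and on it the control arm would not be emptied. It is not established, however: section 10.6 lists AE reporting among the data coordination unit's functions, and nowhere do the documents say that unrelated AEs enter WebDCU. Sites could follow either reading.

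A reader might infer more than the text supports:

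- *That the control count is fixed at zero.* This needs the database reading, and also that no control event is ever attributed to study participation.
- *That the AE table could not show a difference.* The filter tends to produce one, to the disadvantage of SET; the trouble is that it could not be interpreted.
- *That the trial loses its safety comparison altogether.* SAEs are reported regardless of relatedness, and all SAEs are compared across groups in both documents. Only the related-SAE half of that comparison has little meaning in an untreated arm.
- *That nothing could be said about duration.* Related AEs pass the same filter in all three SET arms and can be described across them, subject to the attribution judgement. Session completion, with its 80% criterion, is a separate tolerability measure.

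It is also fair to say that the endpoint never promised an all-cause comparison of non-serious AEs, that the protocol regards the intervention as low-risk, and that charting keeps the events recoverable. But no retrieval from charts is planned, and section 9.4.6 does promise a summary of all AEs.

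**Conclusion.** The point holds in two parts.

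The first is conditional. If reporting in 8.2.3 means entry in the trial database, non-serious AEs cannot be compared interpretably between SET and no SET. The artefact is about 1 to 25 percentage points over the assumed ranges. Those ranges are illustrative, and no single value within them should be quoted as expected. That the judgement is unblinded is an inference from section 4.1.1.

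The second is unconditional. SAP section 12 omits the non-serious AEs that protocol section 9.4.6 says are summarised, and with them the related-AE component of the section 3.0 endpoint.

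This should be corrected, because it decides what the trial can say about non-serious harm. It does not touch the primary efficacy analysis or the all-SAE comparison.

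**What to change.** - **Protocol 8.2.3:** state that every AE elicited in any of the four arms is entered in WebDCU, with seriousness, severity and relatedness recorded as attributes. Confine the relatedness condition to expedited or IRB reporting, and name the recipient.
- **SAP 12:** tabulate all-cause non-serious AEs and SAEs by arm. Keep the existing comparison of all SAEs. Show relatedness descriptively for the SET arms.
- **Consistency:** align protocol sections 3.0, 8.2.3 and 9.4.6 with SAP 12, so that the safety endpoint, its collection and its analysis cover the same events.

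The cost is a few lines of text and a small amount of extra data entry for events that are already asked about weekly and charted. If all AEs already go into WebDCU, only the wording and the SAP tables change.
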